6.1.7. Derived Variables

- IGA average score = in protocol version 1.0, IGA was assessed by body area (chest/abdomen, back, arms, and legs). Under protocol version 2.0, this was changed to a global (overall) assessment. For comparability, the average of the body area IGA results will be taken to yield one score for subjects enrolled under protocol version 1.0. Scores will range from 0 to 4. Higher scores indicate worse disease.
- VIIS total score = sum of the individual body area scaling scores, with a range of 0 to 16. Each individual item is scored on a scale of 0-4, where 0 = normal skin; no perceptible scale or smoothening and 4 = confluent, primarily large, thick scales. Higher scores indicate worse scaling.
- Ectropion total score = sum of the 8 individual item scores (lateral apposition, medial apposition, scleral show, conjunctival show, excess tear film, redness of the eye, round canthus, punctum lacrimale), with a range of 0 to 8. Each individual item is scored 0

(nonaffected/no/invisible), 0.5 (≤ 1 mm/emerging), or 1 (affected/yes/visible). Higher scores indicates worse ectropion.

- DLQI total score = sum of the 10 individual item scores, with a range of 0 to 30. Higher scores indicate poorer quality of life.
- CDLQI total score = sum of the 10 individual item scores, with a range of 0 to 30. Higher scores indicate poorer quality of life.
- Number of doses taken = total number of tubes returned – total number of tubes returned unused
- Number of weeks on study = (last day on study – treatment start date + 1) / 7
- Number of expected doses = 2 * number of weeks on study
- Total weight used = total weight of tubes dispensed (grams) – total weight of tubes returned (grams)
- Initial application amount used = tube weight before drug application (grams) – tube weight after drug application (grams), as collected on the initial study drug application CRF
- Compliance by tube weight = total weight used / total weight of tubes dispensed * 100%
- Compliance by number of doses = number of doses taken / number of expected doses * 100%
- Change from baseline = value at current time point – value at baseline.
- TEAE = An AE is defined as treatment emergent if the onset or worsening is at the time of or following the start of the first application of study drug (trifarotene or vehicle) through the Follow-up Visit or Early Termination Visit, whichever occurs first..

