9.1. Adverse Events

All AEs, TEAEs, and SAEs will be coded using the MedDRA dictionary Version 21.1.

Treatment-emergent AEs are defined as:

- AEs with onset at the time of or following the start of treatment with study drug through 14 days after the last application of study drug, or
- AEs starting prior to the start of treatment but increasing in severity or relationship at the time of, or following, the start of treatment with study drug through the last application of study drug.

The causal relationship of the AE to the study drug is determined by the investigator as Not Related, Unlikely Related, Possibly Related, and Related. These will be mapped to Unrelated (Not Related or Unlikely Related) and Related (Possibly Related, or Related).

Adverse event severity grades are reported as mild, moderate, or severe.

Summaries of incidence rates (frequencies and percentages) of individual TEAEs will be presented by SOC, PT, and treatment group for the Double-blind Period and OLE. Such summaries will be displayed for all TEAEs, TEAEs by maximum severity, and TEAEs by relationship.

Each subject will be counted only once within each summation level (SOC and PT). If a subject experiences more than 1 TEAE within each summation level, the TEAE with the strongest relationship or the maximum severity, as appropriate, will be included in the summaries of relationship and severity. If a particular event is missing the severity and/or relationship, then the strongest possible severity or relationship will be assumed for analysis (severity = severe, relationship = related).

Incidences will be presented by descending frequency of SOC and PT within SOC, and then alphabetically within PT where the incidence is the same; this is based on overall subjects then alphabetically in case of a tie.

Missing and partially missing AE start and/or stop dates and times will be imputed, for the purpose of statistical analysis, according to the specifications described in Section 6.1.8.

In the AE data listings, all AEs will be displayed. AEs that are treatment emergent will be flagged.

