9.3. Vital Signs

Vital signs will be collected at Screening, Baseline, Day 14, Day 30, Day 60, Day 90, Day 120, Day 150, Day 180, and Day 194. Descriptive summaries of actual values and changes from baseline will be calculated for systolic blood pressure (mmHg), diastolic blood pressure (mmHg), and pulse (bpm).

The number of subjects with vital sign values below, within, or above normal ranges, by study visit will be tabulated (shift tables) for each parameter by treatment group.

These summaries will be presented by study visit and treatment group. See Section 6.1.1 for the definition of baseline.

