9.5. Local Tolerability

During all clinic visits, the investigator will assess local tolerability (Scale: 0-3 [none, mild, moderate, severe]) for each treated body area (chest/abdomen, back, arms, legs, and face/neck).

Descriptive summaries of the investigator's assessment of erythema, stinging/burning, and pruritus will be presented by body area, period, treatment group, and study visit.

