Subjects with a TEAE Leading to Discontinuation of Study Drug	XX (XX.X%)	XX (XX.X%)	XX (XX.X%)	XX (XX.X%)	XX (XX.X%)
Subjects with an AE leading to Death	XX (XX.X%)	XX (XX.X%)	XX (XX.X%)	XX (XX.X%)	XX (XX.X%)

Abbreviations: AE = adverse event; CRF = case report form; MedDRA = Medical Dictionary for Regulatory Activities; SAE = serious adverse event; TEAE = treatment emergent adverse event.

Note: Percentages are n/Number of subjects in the Safety Population within actual treatment group and overall*100. AEs were coded using MedDRA version 21.1. A TEAE is any AE with an onset at the time of or following the start of treatment with study drug through the Follow-up Visit or Early Termination Visit, whichever occurs first. This will include any AE starting prior to the start of treatment but increasing in severity or relationship at the time of, or following, the start of treatment with study drug through the Follow-up Visit or Early Termination Visit, whichever occurs first.

[1] Subjects are counted only once at the worst severity. If a severity designation is missing, it will be considered as severe.

[2] Subjects are counted only once at the strongest possible relationship. If a relationship designation is missing, the AE will be considered as related. This relationship is categorized for summarization as follows: Related = Related and Possibly Related; Not Related = Not Related and Unlikely Related.

SOURCE: Listing 16.2.7.1

Table 14.3.1.1.2
Overall Summary of Treatment Emergent Adverse Events during the OLE
OLE Safety Population

Same shell as Table 14.3.1.1.1

Programming note: Only include one set of columns for Trifarotene cream HE1 200 ug/g.

Update Note: to read "Note: Percentages are $n/\text{Number of subjects in the OLE Safety population within treatment group} \times 100$. All subjects received Trifarotene cream HE1 200 ug/g in the OLE." Add OLE = open label extension to Abbreviations.

Table 14.3.1.2.1
Incidence of Treatment Emergent Adverse Events during the Double-blind Period by System Organ Class and Preferred Term
Safety Population

System Organ Class Preferred Term	Trifarotene cream HE1 100 ug/g (N=XX)	Trifarotene cream HE1 200 ug/g (N=XX)	Overall Trifarotene cream HE1 (N=XX)	Vehicle (N=XX)	Overall (N=XX)
Subjects with at least 1 TEAE	XX (XX.X%)	XX (XX.X%)	XX (XX.X%)	XX (XX.X%)	XX (XX.X%)
System Organ Class 1	XX (XX.X%)	XX (XX.X%)	XX (XX.X%)	XX (XX.X%)	XX (XX.X%)
Preferred Term 1	XX (XX.X%)	XX (XX.X%)	XX (XX.X%)	XX (XX.X%)	XX (XX.X%)

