Category 3	XX (XX.X%)	XX (XX.X%)	XX (XX.X%)	XX (XX.X%)	XX (XX.X%)
Day 90					
Category 1	XX (XX.X%)	XX (XX.X%)	XX (XX.X%)	XX (XX.X%)	XX (XX.X%)
Category 2	XX (XX.X%)	XX (XX.X%)	XX (XX.X%)	XX (XX.X%)	XX (XX.X%)
Category 3	XX (XX.X%)	XX (XX.X%)	XX (XX.X%)	XX (XX.X%)	XX (XX.X%)

Note: Percentages are n/Number of subjects in the ITT population within randomized treatment group and overall*100.
[1] Baseline is defined as the last non-missing assessment recorded prior to the first dose of treatment in the Double-blind Period.
SOURCE: Listing 16.2.8.4

Table 14.3.5.4.3.2
Laboratory Data: Summary of Qualitative Urinalysis Parameters by Study Visit
OLE Safety Population

Same shell as Table 14.3.5.4.3.1

Programming note: Only include one set of columns for Trifarotene cream HE1 200 ug/g. Update Note: to read "Subjects are summarized by treatment group. All subjects received Trifarotene cream HE1 200 ug/g in the OLE." Visits will be Baseline, Day 120, and Day 180. Add OLE = open label extension to Abbreviations.

Table 14.3.6.1.1
Summary of Vital Signs by Study Visit
Safety Population

Same shell as Table 14.3.5.1.1.1

Programming note: Visits include Baseline [1], Days 14, 30, 60, and 90. Parameters include weight (kg), BMI (kg/m²), systolic blood pressure (mmHg), and diastolic blood pressure (mmHg). Include derivation of BMI in Note: Body Mass Index (BMI) = weight (kg) / [height (m)]². Update SOURCE: to Listings 16.2.9.1

Table 14.3.6.1.2
Summary of Vital Signs by Study Visit
OLE Safety Population

Same shell as Table 14.3.5.1.1.1

Programming note: Only include one set of columns for Trifarotene cream HE1 200 ug/g. Update Note: to read "Subjects are summarized by treatment group. All subjects received Trifarotene cream HE1 200 ug/g in the OLE." Visits include Baseline [1], Days 120, 180, and 194. Parameters include weight (kg), BMI (kg/m²), systolic blood pressure (mmHg), and diastolic blood pressure (mmHg). Include derivation of BMI in Note: Body Mass Index (BMI) = weight (kg) / [height (m)]². Add OLE = open label extension to Abbreviations. Update SOURCE: to Listings 16.2.9.1

Table 14.3.6.2.1
Summary of 12-Lead Electrocardiogram by Study Visit
Safety Population

Same shell as Table 14.3.5.1.1.1

Programming note: Visits include Baseline [1], Days 30 and 90. Parameters include heart rate (bpm), PR interval (ms), QRS interval (ms), uncorrected QT interval (ms), and QTcF (ms). Update SOURCE: to Listings 16.2.9.2

Table 14.3.6.2.2

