Severe	XX (XX.X%)	XX (XX.X%)	XX (XX.X%)	XX (XX.X%)	XX (XX.X%)
Stinging/Burning					
None	XX (XX.X%)	XX (XX.X%)	XX (XX.X%)	XX (XX.X%)	XX (XX.X%)
Mild	XX (XX.X%)	XX (XX.X%)	XX (XX.X%)	XX (XX.X%)	XX (XX.X%)
Moderate	XX (XX.X%)	XX (XX.X%)	XX (XX.X%)	XX (XX.X%)	XX (XX.X%)
Severe	XX (XX.X%)	XX (XX.X%)	XX (XX.X%)	XX (XX.X%)	XX (XX.X%)
Pruritus					
None	XX (XX.X%)	XX (XX.X%)	XX (XX.X%)	XX (XX.X%)	XX (XX.X%)
Mild	XX (XX.X%)	XX (XX.X%)	XX (XX.X%)	XX (XX.X%)	XX (XX.X%)
Moderate	XX (XX.X%)	XX (XX.X%)	XX (XX.X%)	XX (XX.X%)	XX (XX.X%)
Severe	XX (XX.X%)	XX (XX.X%)	XX (XX.X%)	XX (XX.X%)	XX (XX.X%)

Note: Percentages are n/Number of subjects in the Safety population within actual treatment group and overall*100.
[1] Baseline is defined as the last non-missing assessment recorded prior to the first dose of treatment in the Double-blind Period.
SOURCE: Listing 16.2.9.3

Programming note: Continue for Back, Arms, and Legs. Visits will be Baseline [1], Day 14, Day 30, Day 60, and Day 90.

Table 14.3.6.3.2
Summary of Local Tolerability Assessments by Study Visit
OLE Safety Population

Same shell as Table 14.3.6.3.1

Programming note: Continue for Back, Arms, and Legs. Visits will be Baseline [1], Day 104, Day 120, and Day 150. Update Note: to read "Note: Percentages are n/Number of subjects in the OLE Safety population within treatment group*100. All subjects received Trifarotene cream HE1 200 ug/g in the OLE." Add OLE = open label extension to Abbreviations.

Table 14.3.6.4.1
Summary of Physical Examination Results by Study Visit
Safety Population

Study Visit: XXXXX

Body System Result Clinically Significant?	Trifarotene cream HE1 100 ug/g (N=XX)	Trifarotene cream HE1 200 ug/g (N=XX)	Overall Trifarotene cream HE1 (N=XX)	Vehicle (N=XX)	Overall (N=XX)
Body System 1					
Not Done	XX (XX.X%)	XX (XX.X%)	XX (XX.X%)	XX (XX.X%)	XX (XX.X%)
Normal	XX (XX.X%)	XX (XX.X%)	XX (XX.X%)	XX (XX.X%)	XX (XX.X%)
Abnormal	XX (XX.X%)	XX (XX.X%)	XX (XX.X%)	XX (XX.X%)	XX (XX.X%)
Yes	XX (XX.X%)	XX (XX.X%)	XX (XX.X%)	XX (XX.X%)	XX (XX.X%)
No	XX (XX.X%)	XX (XX.X%)	XX (XX.X%)	XX (XX.X%)	XX (XX.X%)
Body System 2					
Not Done	XX (XX.X%)	XX (XX.X%)	XX (XX.X%)	XX (XX.X%)	XX (XX.X%)
Normal	XX (XX.X%)	XX (XX.X%)	XX (XX.X%)	XX (XX.X%)	XX (XX.X%)
Abnormal	XX (XX.X%)	XX (XX.X%)	XX (XX.X%)	XX (XX.X%)	XX (XX.X%)
Yes	XX (XX.X%)	XX (XX.X%)	XX (XX.X%)	XX (XX.X%)	XX (XX.X%)
No	XX (XX.X%)	XX (XX.X%)	XX (XX.X%)	XX (XX.X%)	XX (XX.X%)
...					

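### Sections 6.1.7 and 9.1 give two incompatible TEAE windows, with the AE shells following 6.1.7; the tolerability and vital-sign shells also omit summaries that Section 9 promises

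*SAP*

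**What the plan says.** **TEAE window.** Section 6.1.7 (Derived Variables) counts onset or worsening from the first application "through the Follow-up Visit or Early Termination Visit, whichever occurs first". The footnotes of the AE shells in Section 14.2 and of Listing 16.2.7.1 carry the same limit: "treatment with study drug through the Follow-up Visit or Early Termination Visit, whichever occurs first". Section 9.1 (Adverse Events) sets a different one. Onset counts "following the start of treatment with study drug through 14 days after the last application of study drug", while worsening of an event that began before treatment counts only as far as the last application.

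**Local tolerability.** Section 2.2.1 names this as a safety endpoint for five body areas. Section 9.5 has it assessed "for each treated body area (chest/abdomen, back, arms, legs, and face/neck" and promises summaries by area, period, arm and visit. Table 2 (OLE schedule) marks it at Days 104, 120, 150 and 180. The shell for Table 14.3.6.3.1 prints chest/abdomen and continues only with back, arms and legs. The OLE shell, Table 14.3.6.3.2, says: "Continue for Back, Arms, and Legs. Visits will be Baseline [1], Day 104, Day 120, and Day 150".

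**Vital signs.** Section 9.3 promises summaries of "systolic blood pressure (mmHg), diastolic blood pressure (mmHg), and pulse (bpm" and includes Day 150 among its visits. The note for Table 14.3.6.1.1 reads "Visits include Baseline [1], Days 14, 30, 60, and 90. Parameters include weight (kg), BMI" and goes on to systolic and diastolic pressure, without pulse. Table 14.3.6.1.2 has the same parameters and lists Days 120, 180 and 194 for the OLE.

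**The concern.** The TEAE flag decides which events enter every AE incidence table. Two definitions in the body of one SAP cannot both be programmed, and the shells are what a programmer works from, so tables built from them would not match Section 9.1. Comparing safety between arms is part of the primary objective (Section 2.1.1), and safety over up to 180 days is a secondary objective (Section 2.1.2). Section 1 says the plan is filed before any unblinded analysis. If the conflict is found only after unblinding, the choice of window could be influenced by the results.

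The tolerability and vital-sign gaps are simpler. The plan promises summaries in Section 9 and then specifies tables that leave part of them out. One of the five areas of a named safety endpoint would never be compared by arm, and the OLE end-of-treatment tolerability visit would not be tabulated.

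**Working it through.** There is no plan figure to reproduce. The check sets the texts side by side and counts days.

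**1. TEAE window.** Let L be the day of the last application and V the day of the Follow-up or ET Visit, whichever is earlier.

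- Section 9.1: onset window ends at L + 14; worsening window ends at L.
- Section 6.1.7 and shells: both windows end at V.
- Difference (6.1.7 minus 9.1): V − L − 14 days for onset; V − L days for worsening.

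The days below are assumed for illustration, except that Table 2 puts the OLE Follow-up at Day 194 or 14 days after the end of open-label treatment.

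| Case | Event | 9.1 ends | 6.1.7 ends | 6.1.7 relative to 9.1 |
|---|---|---|---|---|
| A. Last application Day 30, ET Visit Day 33 | onset | 30 + 14 = Day 44 | Day 33 | 11 days shorter |
| A. | worsening | Day 30 | Day 33 | 3 days longer |
| B. Drug stopped Day 30, visits continue to Day 90 | onset | Day 44 | Day 90 or later | at least 90 − 44 = 46 days longer |
| B. | worsening | Day 30 | Day 90 or later | at least 90 − 30 = 60 days longer |
| C. OLE completer, last application about Day 180 | onset | Day 194 | Day 194 | none |
| C. | worsening | Day 180 | Day 194 | 14 days longer |

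Case B can occur because note b to Table 1 keeps Day 90 on schedule for subjects who stop drug but go on attending.

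For an ET Visit g days after the last application (g below 14), the onset loss is 14 − g days, at most 14.

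**2. Where the onset loss has recorded data behind it.** Table 2 has an ET column (shared with Day 180) and a separate Follow-up column, with adverse events marked in both. For an OLE early terminator the ET Visit comes first. A new event that starts after that visit, within 14 days of the last application, and is recorded at Follow-up is a TEAE under Section 9.1 and not under Section 6.1.7.

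**3. Shell coverage.**

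| Item | Promised | In the shells | Missing |
|---|---|---|---|
| Tolerability areas | 5 | 4 | face/neck, both periods |
| OLE on-treatment tolerability visits | Days 104, 120, 150, 180 | Days 104, 120, 150 | Day 180 |
| Vital-sign parameters (Section 9.3) | 3 | 2 | pulse, both periods |
| OLE vital-sign visits (Section 9.3) | Days 120, 150, 180, 194 | Days 120, 180, 194 | Day 150 |

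The shells also list weight and BMI, but Table 1 schedules these only at Screening and Day 90 and Table 2 has no such row, so most of those cells would be empty.

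**The case against.** A reader might infer that the shells under-report safety events. The document does not support that as a general statement.

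- **Direction.** Cases B and C show the 6.1.7 window running longer for subjects who stop drug but stay on study and for worsening of pre-treatment events. Only onsets after an ET Visit held within 14 days of the last application are lost.
- **Size.** One could apply the 20% drop-out/nonevaluable rate to the 65 subjects enrolled and reach 0.20 × 65 = 13 subjects and 13 × 14 = 182 subject-days. That is an extreme bound, not an estimate. The rate is a planning figure that mixes dropout with non-evaluability and was set for 120 subjects, and the product needs every ET Visit to fall on the day of the last application. The SAP gives no actual number of early terminators.
- **Data.** In the Double-blind Period, Day 90 doubles as the ET visit. The only later contact shown is a telephone call, for subjects not entering the OLE, about adverse events that are ongoing. Collection of new events after a Double-blind ET Visit is not shown, so a longer window may recover little there.
- **Omissions.** Listing 16.2.7.1 holds all AEs, Listing 16.2.9.3 prints face/neck and Listing 16.2.9.1 prints pulse. ECG heart rate is tabulated at Baseline and Days 30, 90, 120 and 180, which partly covers pulse. Section 9.5 already commits to summaries by body area.

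All of this stands, and it limits the point to inconsistency and missing summaries. It does not remove the point. A by-subject listing gives no comparison by arm, and the SAP text at hand does not say whether the sections or the shells prevail. Nor is the TEAE conflict merely one of shells against text, since it lies between two sections of the body.

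**Conclusion.** The point holds as an internal contradiction plus incomplete shells, and it should be corrected. Sections 6.1.7 and 9.1 define different TEAE windows for both onset and worsening, and the AE tables would follow the former. The onset loss is at most 14 days per subject whose ET Visit falls less than 14 days after the last application, and it is clearest for OLE early terminators with an event recorded at Follow-up. The opposite effect can be larger: at least 46 days for onset in case B, under its assumed days. The net effect on TEAE counts cannot be determined from the document.

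The shell gaps are definite but small: one of five tolerability areas, one of four OLE on-treatment tolerability visits, one of three vital-sign parameters and one OLE vital-sign visit. They are missing summaries, not lost data.

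**What to change.** Before unblinding:

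1. Choose one TEAE window covering both onset and worsening, for example from first application to 14 days past the last one. State it identically in Sections 6.1.7 and 9.1, all AE table footnotes and Listing 16.2.7.1. This example has a small downside: later AEs in subjects who stop drug but stay on study, which Section 6.1.7 now counts, would appear only in the listing. It also lengthens the worsening window now in Section 9.1. Both effects should be acknowledged in the text.
2. Add Face/Neck to Tables 14.3.6.3.1 and 14.3.6.3.2, and Day 180 to the latter.
3. Add pulse to Tables 14.3.6.1.1 and 14.3.6.1.2, and Day 150 to the latter.

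While editing these shells, note that Section 9.3 also promises vital-sign shift tables that Table 11 does not list.

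The cost is SAP and shell wording plus the matching programming. The tolerability and vital-sign items are already in the schedules and listings, so items 2 and 3 need no new data. Item 1 works with whatever AE data were collected.

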6.1.8. Data Adjustments/Handling/Conventions

All collected data will be presented in listings. Data not subject to analysis according to this plan will not appear in any tables or graphs but will be included only in the data listings.

All *P* values will be displayed in 4 decimals and rounded using standard scientific notation (e.g., 0.XXXX). If a *P* value less than 0.0001 occurs it will be shown in tables as <0.0001.

Adverse events will be coded using the MedDRA version 21.1 thesaurus. Concomitant mediations will be coded using the WHO-DD version September 2018.

A treatment-related AE is any AE with a relationship to the study drug of possibly related and related.

If partial AE or medication dates occur, the convention for replacing missing dates for the purpose of statistical analysis is as follows:

For partial AE and medication start dates:

- If the year is unknown, then do not impute the date but assign a missing value.
- If the year is known, but the month or month and day is unknown, then:
 - If the year matches the year of first dose date and the end date (if present) is after first dose date, then impute as the month and day of the first dose date.
 - Otherwise, assign 01 January.
- If the year and month are known, but the day is unknown, then:
 - If the month and year match the month and year of the first dose date, then impute as the day of the first dose date.
 - Otherwise, assign 01.

For partial AE and medication end dates:

- If the year is unknown, then do not impute the date but assign as missing value.
- If the year is known, but the month or month and day is unknown, then:
 - If the year matches the year of the last date of the study (date of last contact if subject lost to follow-up; date of completion or early termination otherwise), then impute as the month and day of the last date of the study.
 - Otherwise, assign 31 December.
- If the year and month are known, but the day is unknown, then:
 - If the month and year match the month and year of the last date of the study, then impute as the day of the last date of the study.
 - Otherwise, assign the last day of the month.

If partial times occur, the convention is as follows:

- if the missing time occurs on the day of the first dose and both the hour and minute are missing then the time assigned is the time of the first dose, otherwise if both the hour and minute are missing and the date is not the date of first dose the time assigned is 12:00;
- if the date is the same as the date of the first dose and

- only hour is missing the hour assigned is 12 or the hour of first dose, whichever is later;
- only the minute is missing the minute assigned is 30 or the minute of first dose, whichever is later;
- Otherwise if the date is not the same as the date of first dose, the hour assigned is 12 if the hour is missing and the minute assigned is 30 if the minute is missing.

7. Study Subjects and Demographics

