9.7. Concomitant Medication

Prior and concomitant medications, coded using World Health Organization-Drug Dictionary Enhanced (WHO-DDE) (September 2018), will be summarized descriptively by Anatomical Therapeutic Chemical (ATC) classification Level 4 and PT (i.e., ATC classification Level 5), if applicable, using counts and percentages for the Safety Population.

Prior medications and concomitant medications will be presented separately. The assignment of medications as prior and/or concomitant will be done as follows:

- **Prior medications:** Medications that started before the first dose of study drug will be considered prior medications whether or not they were stopped before dose.
- **Concomitant medications:** Any medications continuing or starting after the first dose of study drug through the end of study will be considered to be concomitant.

If a medication starts prior to the first dose and continues after the first dose it will be considered both prior and concomitant. Prior and concomitant medications will also be listed. Prior and concomitant medications will be summarized descriptively by treatment using counts and percentages.

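### Partial start dates (SAP 6.1.8): when only the day is missing, the first-dose day is imputed without checking the end date, so a medication that ended before dosing can lose its prior status

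*SAP*

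**What the plan says.** Section 6.1.8 of the SAP sets one convention, headed "For partial AE and medication start dates", with separate branches by what is missing.

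- **Month, or month and day, unknown.** The first-dose month and day are used under this condition: "If the year matches the year of first dose date and the end date (if present) is after first dose date". Otherwise the start is 01 January.
- **Only the day unknown.** "If the month and year match the month and year of the first dose date, then impute as the day of the first dose date". Failing that, the start is the first of the month. The end date is not mentioned.

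The same section covers a missing clock time, under the rule beginning "if the missing time occurs on the day of the first dose and both the hour and minute are missing then the time assigned"; the value used there is the first-dose time.

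These dates feed two classifications. Section 9.7: "Medications that started before the first dose of study drug will be considered prior medications". Section 6.1.7 makes an adverse event treatment-emergent if "onset or worsening is at the time of or following the start of the first application of study drug", and Section 9.1 likewise counts "AEs with onset at the time of or following the start of treatment with study drug through 14 days after the last application". Section 9.1 sends partial adverse event dates back to Section 6.1.8 and adds no check of its own.

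**The concern.** Imputing the first-dose day is a sensible default when nothing shows whether a record began before or after dosing. It is not sensible when the record's own end date shows that it was over before the first application. The SAP recognises this in the month-unknown branch and omits it in the day-unknown branch. In that case the rule produces a start after the end, and a record that was certainly pre-treatment is classified as if it were not.

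At stake is the content of the prior-medication table (14.1.4), possibly the concomitant-medication table (14.3.6.5.1), and in principle the treatment-emergent flag for an adverse event.

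**Working it through.** The SAP states no figure here, so the check applies the written rule to dates.

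**Inputs.** The two start-date branches and the time rule (Section 6.1.8), the treatment-emergent definitions (Sections 6.1.7 and 9.1), and the prior and concomitant definitions (Section 9.7). The dates are illustrative: first dose 20 June 2020.

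| Record | Imputed start as written | Start after end? | Before first dose? |
|---|---|---|---|
| Day unknown, June 2020; ended 10 June | 20 June 2020 | Yes, by 20 − 10 = 10 days | No |
| Month and day unknown, 2020; ended 10 June | 01 January 2020 | No | Yes |
| Day unknown, June 2020; ended 25 June | 20 June 2020 | No | No |
| Day unknown, June 2020; ongoing | 20 June 2020 | No | No |

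Row 1 is the defect. Row 2 has the same end date and a less complete start, yet is classified correctly. Rows 3 and 4 are the ordinary conservative imputation and are not in question.

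**Consequence for row 1.** As a medication, its start is no longer before first dose, so it is not prior. It ended before dosing, so it is not continuing; and a start equal to the first-dose date is not clearly after it. It may therefore fall into neither table, or be counted as concomitant, depending on how the comparison is programmed. Listing 16.2.9.5 offers only prior, concomitant or both. As an adverse event, a missing time would be set to the first-dose time, so onset would fall at the start of treatment and the event would be flagged.

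**Scope of the branch.** Let the first dose be on day *f* of the month and the known end on day *e* < *f*. The imputed start is day *f*, which is always later than *e*. In a 30-day month there are 0 + 1 + … + 29 = 30 × 29 / 2 = 435 such pairs, and all 435 give a start after the end. With an end-date condition that falls back to day 01, none do: *e* is at least 1, so 01 is never after the end, and *f* is at least 2, so the record is prior. The 435 shows that the failure is systematic within this set. It says nothing about how often such records occur.

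**Boundary.** If the end day is also missing, Section 6.1.8 moves the end to the last day of the month (or to the last study date, if that is in the same month), and no contradiction in dates arises. The defect needs a known end date.

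**The case against.** The strongest case on the other side concerns reach, and most of it stands.

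- **Adverse events.** Table 1 collects them from Baseline, and study drug is first applied that day after the baseline measurements. An event that began and resolved earlier would not normally be recorded. Section 9.1 does provide for events starting before treatment, so the case is possible, but it should be rare.
- **Washed-out treatments.** A reader might infer that the washout of up to 90 days makes the problem common. The documents do not support that. The branch looks at the start month, so the record must both start and end in the calendar month of first dose. Treatments being washed out would usually have started in an earlier month. Short courses begun late in Screening are the likelier candidates.
- **Per-protocol population.** A reader might also infer that such a record would look like prohibited use on study and cost a subject per-protocol status. Section 7.2 bases those exclusions on a blinded sponsor review of the data, Section 6.1.8 confines imputation to statistical analysis, and the shell for Listing 16.2.9.5 shows a start date with the day left blank. Nothing derives per-protocol status from imputed medication dates.
- **Inference.** Section 9 plans no formal inference for safety variables, and efficacy does not use these dates.

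None of this removes the inconsistency. No rule in Sections 6.1.7, 6.1.8, 9.1 or 9.7 overrides the day-unknown branch or prevents a start from falling after an end.

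**Conclusion.** The point holds as a minor error in a stated rule. Applied literally, the day-unknown branch gives an impossible date to every record whose start falls in the first-dose month with the day missing and whose known end falls in that month before dosing. The main effect is that a medication certainly taken before treatment leaves the prior-medication table and may be miscounted as concomitant. The adverse event version follows from the same text but should be rare.

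The SAP gives no count of affected records. Among the 65 enrolled subjects it may be very small or zero. The conclusion assumes that the program follows the text with no unwritten check of start against end. It reaches descriptive tables only; no effect on the per-protocol population or on efficacy is shown.

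**What to change.** Add an end-date condition to the day-unknown branch of Section 6.1.8, for example: *where month and year are those of first dose and the end date, if present, is on or after first dose, use the first-dose day; otherwise assign 01.*

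The existing month-unknown branch requires an end after first dose, which would treat a record ending on the first-dose day differently from this wording. Choose either after or on or after, and use it in both branches.

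In the example, the start becomes 01 June 2020: before the end, prior, and not treatment-emergent. Records that are ongoing or end after first dose are unchanged. The cost is one clause in the SAP, one matching edit in the neighbouring branch if on or after is chosen, and the corresponding condition in the date-imputation program. It is best done before the SAP is filed, which Section 1 places ahead of any unblinded analysis.
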